6.6.4. Electrocardiogram

For each planned time point, baseline values, absolute values and change from baseline values within each treatment will be summarized with descriptive statistics for each ECG parameter (using Pfizer Data Standards).

A plot of QTcF versus plasma concentration will be generated at nominal time points.

Maximum decrease and increase values and changes from baseline for the ECG parameters QT interval, heart rate, QTc interval, PR interval and QRS interval will be summarized by treatment and time post dose using Pfizer Data Standards.

The number (%) of subjects with maximum post dose QTc values and maximum increases from baseline in the following categories will be tabulated by treatment:

Table 5. Safety QTcF¹

	Borderline (msec)	Prolonged (msec)
Absolute Value	≥450 - <480	≥480
Absolute Change	30-<60	≥60

In addition, the number of subjects with corrected and uncorrected QT values ≥500 msec will be summarized.

ECG endpoints and changes from baseline (QTcF, PR, QRS) will also be summarized descriptively by treatment using categories as defined in Pfizer Data Standards (for QTc, these correspond to ICH E14). Numbers and percentages of subjects meeting the categorical criteria will be provided. All planned and unplanned post dose time points will be counted in these categorical summaries. All values meeting the criteria of potential clinical concern will be listed.

6.6.5. Physical Examination

Physical examination data will be listed and summarized within treatment group in accordance with the Pfizer Data Standards.

6.6.6. Neurological Examination

Neurological examination data will be presented in the listings.

6.6.7. Assessment of Suicidal Ideation and Behavior

6.6.7.1. Columbia Suicide Severity Rating Scale (C-SSRS)

In general, the denominator used in the percentages will be the number of subjects assessed for suicidality or worsening, the denominator would include the subset of subjects who had any level of suicidality reported at baseline. For new onset, the denominator would include the subset of subjects with no suicidality reported at baseline.

A subject listing of C-CASA categories as well as the underlying C-SSRS scale data will be presented.

In addition, a summary table with the number and percent of subjects within each C-CASA category by treatment group at screening, baseline, and at any time post-baseline without regard to baseline will be reported.

6.6.7.2. Mental Health Risk Assessment (MHRA)

A summary table by visit will indicate the number and percent of subjects that met the criteria for MHRA evaluation, whether the MHRA module was performed, and if the subject was either eligible to enter the study (Screening) or eligible to continue in the study (All visits after Screening). The category of subjects that met the criteria for MHRA evaluation will include additional details on the criteria met:

- Screening:
 - PHQ-8 total score ≥ 15 ,
 - Subject answered "YES" on C-SSRS item 4, 5, or any suicidal behavior question on the C-SSRS,
 - Active suicidal ideation (with method and/or plan and/or intent) in the past year,
 - Previous history of suicidal behavior in the past 10 years, and
 - Principal Investigator's Discretion.
- All Visits after Screening:
 - Subject answered "YES" on C-SSRS item 4, 5, or on any suicidal behavior question on the C-SSRS,
 - Principal Investigator's Discretion.

6.6.8. Questionnaire for Impulsive-Compulsive Disorders in Parkinson's Disease – Rating Scale (QUIP-RS)

For each planned time point and item (ie, disorder), baseline values, absolute values and change from baseline values within each treatment will be summarized with descriptive statistics for the 8 different scoring types. Additionally, the number and percentage of subjects with each of the 8 different scoring types will be presented.

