#### **7.2.7. Questionnaire for Impulsive-Compulsive Disorders in Parkinson's Disease – Rating Scale (QUIP-RS)**

The Questionnaire for Impulsive-Compulsive Disorders in Parkinson's Disease – Rating Scale (QUIP-RS) is a brief, patient reported outcome measure designed to assess the severity of symptoms of ICDs and related behaviors reported to occur in Parkinson's disease.

The QUIP-RS has 4 primary questions pertaining to commonly reported thoughts, urges/desires, and behaviors associated with impulsive-compulsive disorder, each applied to the 4 impulsive-compulsive disorders (compulsive gambling, buying, eating, and sexual behavior) and 3 related disorders (medication use, punning, and hobbyism). It uses a 5-point Likert scale (score 0–4 for each question) to gauge the frequency of behaviors, and instructs subjects to answer questions based on behaviors that occurred in the preceding 4 weeks (or any 4-week period in a designated time frame). The QUIP-RS is valid and reliable as a rating scale for impulse control disorders and related disorders in Parkinson's disease, and can be used to support a diagnosis of these disorders, as well as to monitor changes in symptom severity over time.

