The QUIP-RS has 4 primary questions pertaining to commonly reported thoughts, urges/desires, and behaviors associated with impulsive-compulsive disorder, each applied to the 4 impulsive-compulsive disorders (compulsive gambling, buying, eating, and sexual behavior) and 3 related disorders (medication use, punning, and hobbyism). It uses a 5-point Likert scale (score 0–4 for each question) to gauge the frequency of behaviors, and

instructs subjects to answer questions based on behaviors that occurred in the preceding 4 weeks (or any 4-week period in a designated time frame). Each question is anchored with the following five responses: Never (0), Rarely (1), Sometimes (2), Often (3), and Very Often (4). The scoring range for each item (ie, disorder) is 0-16. Scores will be computed for Gambling (0-16), Buying (0-16), Sex (0-16), Eating (0-16) and Total ICD score (0-64). The Total ICD score includes all 4 impulsive-compulsive disorders. Additionally, scores are computed for Hobbyism-punding (combined, 0-32), Compulsive medication use (0-16) and Total QUIP-RS score (0-112). The Total QUIP-RS score includes all 7 disorders. The higher score indicates a greater level of the Impulsive-Compulsive Disorder.

The general principle of allowing up to 20% of missing responses is applied. Therefore, the following subscores are set as missing if any of the pertaining 4 primary questions has a missing response: Each of the four ICDs (compulsive gambling, buying, eating and sexual behavior) and compulsive medication use. For the hobbyism-punding subscore that has 8 items, 1 missing response is allowed. For the Total ICD score that has 16 items, up to 3 missing responses are allowed. For the Total QUIP-RS score that has 28 items, up to 5 missing responses are allowed. This rule allows for the derivation of total scores even when some of the subscores are missing. With the presence of allowable missing responses, any sub or total will be calculated as follows:

$$(\text{Sum of the nonmissing item scores}) \times \frac{\text{total number of items}}{\text{number of nonmissing items}}$$

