3.5.9. Physician Withdrawal Checklist (PWC-20)

The PWC-20 is a physician-completed, 20-item reliable and sensitive instrument for the assessment of benzodiazepine discontinuation symptoms. The PWC-20 is collected after the completion of study treatment and also at the first visit of follow-up.

Determine the number of subjects with each symptom present (eg, mild or higher severity) and categorize each subject by severity (eg, mild, moderate, and severe). Only non-missing items are considered in summary presentations, and will establish the denominator.

The total PWC-20 score is the sum of 20 item-scores and ranges between 0 and 60. The higher score indicates more frequent/severe symptoms. If more than 5 of the 20 individual items are missing then the total PWC-20 score will be set to missing.

If more than 5 items are missing, the total PWC-20 score is missing; otherwise, the total PWC-20 score will be imputed as follows: sum of the non-missing items X (total number of items)/ (number of items non-missing).

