5.2.2. Analyses for Continuous Data

Descriptive statistics n, mean, median, standard deviation, minimum, and maximum will be used to summarize the endpoints. The differences of each PF-06649751 treatment versus the placebo group with 90% confidence intervals from the fitted model will be reported.

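### SAP 6.6.8 gives no event definition for its QUIP-RS percentage, and no stated QUIP-RS table counts subjects who newly developed or worsened in impulse-control behaviour

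*SAP*

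**What the plan says.** Protocol 2.4.2.1 lists the QUIP-RS among the secondary safety endpoints. Protocol 7.2.7 says that the instrument "can be used to support a diagnosis of these disorders, as well as to monitor changes in symptom severity over time".

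SAP 3.5.8 defines eight scores. For the first five, "Scores will be computed for Gambling (0-16), Buying (0-16), Sex (0-16), Eating (0-16) and Total ICD score (0-64" points; for the other three, "scores are computed for Hobbyism-punding (combined, 0-32), Compulsive medication use (0-16) and Total QUIP-RS score (0-112" points. The only guide to interpretation is the direction: "The higher score indicates a greater level of the Impulsive-Compulsive Disorder".

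SAP 6.6.8 plans two outputs. The first is a by-visit summary: "baseline values, absolute values and change from baseline values within each treatment will be summarized with descriptive statistics for the 8 different scoring types". The second is that "the number and percentage of subjects with each of the 8 different scoring types will be presented". For continuous data, SAP 5.2.2 spells out the first kind of summary: "Descriptive statistics n, mean, median, standard deviation, minimum, and maximum will be used to summarize the endpoints".

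The neighbouring safety scales have event definitions. For the PWC-20, SAP 3.5.9 says: "Determine the number of subjects with each symptom present (eg, mild or higher severity". For the C-SSRS, SAP 3.5.7.1 defines new onset and worsening relative to baseline, and SAP 6.6.7.1 gives each its own denominator.

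**The concern.** A percentage of subjects needs a yes/no outcome for each subject. A score that runs from 0 to 16 or from 0 to 112 is not such an outcome, and neither document says which values would make a subject count. Two programmers could build different tables from the same sentence, and neither table would separate behaviour that began on treatment from behaviour already present on Day 0.

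What is at stake is the main question for this scale in a trial of a dopamine agonist: how many subjects in each arm newly developed or worsened in an impulse-control behaviour. If only a few do, a by-visit mean moves little and the median may not move at all. The maximum shows that at least one subject rose, but not how many.

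**Working it through.** **Inputs from the plan.** The score ranges reproduce. Each disorder has 4 questions scored 0-4, so 4 x 4 = 16. Hobbyism-punding has 8 items: 8 x 4 = 32. Total ICD has 16 items: 16 x 4 = 64. Total QUIP-RS has 28 items: 28 x 4 = 112. All eight are scores with a value for every scored subject. Arm sizes follow from the allocation in SAP 2.2:
- 15 mg: 54 x 2/3 + 144 x 1/8 = 36 + 18 = 54.
- Placebo: 54 x 1/3 + 144 x 1/8 = 18 + 18 = 36.
- 1, 3 and 7 mg: 144 x 2/8 = 36 each.

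The documents give no QUIP-RS distribution, so the case counts and rises below are assumptions.

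**What the percentage could mean.** Take an arm of 36, all scored. Ten have a low, stable, non-zero score from Day 0. Three start at 0 and rise by 12. The other 23 stay at 0.

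| Reading | Calculation | Result |
|---|---|---|
| A score is available | 36/36 | 100% |
| On-treatment score above 0 | (10 + 3)/36 | 36.1% |
| On-treatment score above own Day 0 score | 3/36 | 8.3% |
| New onset among Day 0 zero scores | 3/(36 - 10) = 3/26 | 11.5% |

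Now take a second arm with 13 stable low scorers and no new case. The first two readings again give 100% and 13/36 = 36.1%; the last two give 0%. So under either reading that the present sentence allows, an arm with three large new rises and an arm with none look the same. If the score-above-zero percentage were also shown at Day 0, the first arm would move from 10/36 = 27.8% to 36.1%. That would show a net shift, but not which subjects moved or how far. The sentence does not say whether it applies by time point.

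**What the descriptive statistics show.** If *k* of *n* subjects rise by *d* and the rest are unchanged, the mean change is *k* x *d* / *n*.

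| Arm | Cases, rise | Mean | Median | SD | Maximum | Share affected |
|---|---|---|---|---|---|---|
| 54 | 1, 12 points | 0.22 | 0 | 1.63 | 12 | 1.9% |
| 54 | 3, 12 points | 0.67 | 0 | 2.77 | 12 | 5.6% |
| 36 | 3, 12 points | 1.00 | 0 | 3.36 | 12 | 8.3% |

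For 1 to 4 cases and rises of 8 to 16 points, the mean runs from 0.22 to 1.78 in an arm of 36 (2.8% to 11.1% affected) and from 0.15 to 1.19 in an arm of 54 (1.9% to 7.4%). The median is 0 throughout.

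The maximum is the same for one case and for three. Mean and SD differ, but they point to a count only if everyone else is unchanged. If the other 33 of 36 subjects each fall by 1 point, the mean is (3 x 12 - 33)/36 = 0.08 with the same three large rises.

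By-visit output also splits cases that peak at different times. If one subject of 54 is up 12 points at Week 5, another at Week 10 and a third at Week 15, each visit shows a mean of 12/54 = 0.22 and a maximum of 12. The on-treatment total is 3/54 = 5.6%.

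**The adverse-event route.** SAP 3.5.1 defines no Tier-1 events. Tier-2, which brings risk differences, needs at least 4 subjects with the same preferred term in an arm. At an assumed true rate of 5%, the binomial chance of 4 or more is 10% for 36 subjects and 28% for 54. Over rates of 3% to 10% it is 2% to 49% and 8% to 80%. Tier-3 has no minimum, so a single reported event is still tabulated.

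**The case against.** The strongest reply is that the plan already shows more than its last sentence on this scale suggests.

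- A reader might infer that the scale is summarised by means alone. SAP 5.2.2 does not support that: median, SD, minimum and maximum are included, for each disorder on its own range and for change from baseline. In the 3-of-54 example the table would show a maximum change of 12 and an SD of about 2.8, against 0 and 0 in an unchanged arm.
- A reader might infer that new cases would appear in no table. That goes too far for the same reason, and because an impulse-control event reported as an AE is tabulated under SAP 3.5.1 and 6.6.1 even if it occurs once. The treatment-emergent definition requires it to be new or worse.
- A reader might infer that the percentage carries no information. That follows only from the literal reading; counted as score above zero, it would carry some.
- A reader might infer that no threshold exists. Protocol 9.4 names the QUIP-RS among data whose abnormalities of potential clinical concern are set by Pfizer Data Standards. Those standards are not in the documents, so the absence of a threshold cannot be shown.

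In addition, the scale enters no decision rule, SAP 6.6.1 calls safety analysis generally exploratory, and an external committee reviews unblinded safety data.

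All of this stands and limits the point. It does not supply the missing count. The AE route depends on someone reporting an event, and neither document links a QUIP-RS rise to an AE assessment, whereas Protocol 7.7.1 makes that link for positive C-SSRS answers. Protocol Appendix 2 has no QUIP-RS entry, and SAP 3.5.8 and 6.6.8 do not carry over any threshold.

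**Conclusion.** The point holds in a limited form. The percentage in SAP 6.6.8 has no defined event and is not interpretable as written. No QUIP-RS table stated in the documents counts how many subjects per arm newly developed or worsened. Large rises would show in the maximum, and AE tables would show those reported as AEs, so the harm would not be hidden altogether; what is missing is the number of subjects affected, referenced to Day 0.

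The size depends on assumed inputs. With 3 rises of 12 points, the gap is between a mean change of 0.67 with median 0 and a count of 5.6% in an arm of 54, or between 1.00 and 8.3% in an arm of 36. The lack of an event definition does not depend on those inputs. No efficacy conclusion is affected. This is a cheap improvement to safety reporting, not a design fault.

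**What to change.** Keep the descriptive statistics and replace the last sentence of SAP 6.6.8 with text to this effect:

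> For each of the eight scores and by treatment arm: (a) the number and percentage of subjects whose maximum on-treatment score exceeds their Day 0 score, with the distribution of that maximum increase; and (b) a shift table of Day 0 score (0 versus above 0) against worst on-treatment score, in which new onset uses subjects with a Day 0 score of 0 as the denominator.

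This follows the C-SSRS pattern in SAP 3.5.7.1 and 6.6.7.1. The distribution in (a) is needed because a one-point rise would otherwise count the same as a large one. SAP 5.3 already brings early-termination and unplanned visits into categorical safety determinations; say that this applies here.

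Do not add a diagnostic cut-off or severity bands, since the documents give no source for any. If the Pfizer Data Standards cited in Protocol 9.4 contain a QUIP-RS threshold, state it in the SAP.

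The cost is a short SAP wording change and one more table, settled before unblinding. The Protocol already has the QUIP-RS performed on Day 0 and at Weeks 5, 10 and 15 (sections 6.2.1, 6.2.7, 6.2.10 and 6.2.12). The downside is that the table is descriptive: a rise in score is not a diagnosis.

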6.6.9. Physician Withdrawal Checklist (PWC-20)

Summaries of the count and percentage of patients experiencing each symptom and severity listed in the PWC-20 will be provided by treatment group. Follow the PDS used for reporting incidence and severity of Adverse Events.

The Total PWC-20 score will be presented by treatment group using continuous summary statistics for the raw data.

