6. FSH test at Screening is mandatory for female subjects that do not have documented hysterectomy, bilateral oophorectomy or medically confirmed ovarian failure, to confirm non childbearing potential (see [Section 4.1](#), Inclusion Criteria #3).
7. Hepatitis B antigen, Hepatitis C antibody, and HIV testing.
8. Urine test for drugs of abuse (including THC).
9. Triplicate ECG at all time points.
10. Triplicate vitals (HR and blood pressure) at Screening. Vitals should be collected first while the subject is in the supine position and then in the standing position. Subject temperature must also be assessed at Screening and Day 0 (Randomization) to confirm no symptoms of fever (see Exclusion Criteria #6).
11. Columbia Suicidality Severity Rating Scale (C-SSRS) "Lifetime/Past 12 months" evaluation at Screening, and Columbia Suicidality Severity Rating Scale "Since last evaluation" at all other time points.
12. Refer to [Section 7.2.1](#) for additional safety laboratory tests (blood and urine) to be completed at Screening and Week 17 follow-up visits, and/or as necessary throughout the study after consultation with the Medical Monitor/Sponsor per [Section 7.2.9](#).  
CCI [REDACTED]
14. Prolactin results may be shared with the blinded study team after database release.
15. In addition to compliance verification, subjects will be instructed on which blister card to use for following the week at each phone visit. The verification of blister card may be performed the day following the phone visits.
16. Visits should be scheduled at approximately the same time of day throughout the study. Subjects take their morning dose at home. Subjects will document the timing of PF-06649751 or placebo dose on study visit days.
17. First dose will be administered the morning of Day 1.  
CCI [REDACTED]
19. Diary training and concordance testing will be conducted during the screening visit, as detailed in [Section 7.1.7](#).
20. Subjects will complete an OFF time diary (Hauser diary) for three consecutive days in the week prior to Day 0 (Randomization) Visit and each diary review visit (except the Day 28 visit, in which the OFF time diary will be completed between Day 14 and Day 21 and brought the next clinic visit).
21. UPDRS Part III should be assessed consistently and approximately 2 to 4 hours following L-Dopa dose (except at Screening).

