### **3.1.4. Open Label Extension Study**

Subjects who complete through Week 15 of the B7601003 study will have the option to enroll in an open label extension study (B7601017). If all specified Inclusion/Exclusion criteria are met at Week 10/Screening Visit (B7601017), the subject may exit the current B7601003 study at Week 15/Baseline Visit (B7601017) for continued treatment and follow-up under the open label extension study (B7601017), provided they remain eligible.

Subjects not directly entering study B7601017 at Week 15 must complete the Week 17 and Week 19 Follow-up visits as required per protocol.

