- Register subject as Randomized in IWR system in order to obtain randomization number.
- Dispense Investigational Product. Subjects will begin PF-06649751 or placebo dosing the following morning (Day 1).
- Instruct subjects on continued daily dosing of PF-06649751 or placebo in accordance with randomized dose arm up-titration scheme (see [Table 2](#), Section 5.5.1, [Titration of PF-06649751](#)) and instruct subjects on proper dosing documentation.
- Instruct subjects on continued adjunct stable L-Dopa (open-label) administration.

#### 6.2.2. Dosing: Day 1 through Day 105

- Continued once daily dosing of PF-06649751 or placebo in accordance with randomized dose arm up-titration scheme (see [Table 2](#), Section 5.5.1, [Titration of PF-06649751](#)).
- Continued adjunct stable open-label L-Dopa administration (through Period B).

#### 6.2.3. Titration Period: Day 7

- Dosing compliance verification (Investigational product accountability and documentation) while subject is present to confirm reasons for missed/additional doses. **Based on blister card review and/or tablet count, any subject who is noted not to have taken at least 80% or has taken more than 120% of required doses at any scheduled visit during the study will be considered out of compliance and this must be recorded on the CRF and documented as a Medication Error on the CRF and the source documents.**
- Review and assess adverse events (AEs).
- Assessment of concomitant medications.

- Perform the Columbia Suicidality Severity Rating Scale (C-SSRS) “Since last evaluation”.
- Perform standard supine triplicate 12-lead electrocardiogram (ECG).
- Perform standard single supine and standing vitals (HR and blood pressure).
- Perform MDS-UPDRS Part III.
- Dispense OFF time diary, review instructions including requirement to wait until the next phone visit before completion of the diary.
- Dispense Investigational Product. Next immediate dose level of PF-06649751 or placebo will be taken the next morning.
- Instruct subjects on continued daily dosing of PF-06649751 or placebo in accordance with randomized dose arm up-titration scheme (see [Table 2](#), Section 5.5.1, [Titration of PF-06649751](#)).
- Instruct subjects on continued adjunct stable L-Dopa (open-label) administration.

#### 6.2.4. Titration Period: Day 14

In the case of a phone visit:

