### **7.2.8. Physician Withdrawal Checklist (PWC-20)**

The PWC-20 is a physician-completed, 20-item reliable and sensitive instrument for the assessment of benzodiazepine discontinuation symptoms. It correlates extremely highly with the PWC-35, its parent scale ( $r=0.980$ ). Since most items are also complaints commonly reported by patients as symptoms of anxiety, it is not surprising that the PWC-20 and the Hamilton Anxiety Rating Scale (HAM-A) correlate highly ( $r=0.80$ ) with each other. Therefore, a combination of symptoms and time course, not type of symptoms alone, best differentiate between discontinuation symptoms of rebound/withdrawal and return of anxiety. Discontinuation symptoms occur early and disappear rather swiftly, depending upon speed of taper, daily medication dose, and drug elimination half-life.

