5.3. Methods to Manage Missing Data

For the analysis of safety endpoints, the sponsor data standard rules for imputation will be applied (eg, partial dates for AEs and concomitant medications will be imputed according to Pfizer standard algorithms).

For the Hauser home diary data, an algorithm is used to handle missing 30-minute intervals (See Section 3.1). A summary of missing diary data will be presented by treatment group.

For scales used in this study, scores will be imputed according to the imputation rules and algorithms for missing component scores that are provided in the data standard documents, or scale documentation. Details are included for each endpoint in Section 3.

Efficacy endpoint analyses in this study will be primarily based on observed cases (OC) and missing data will not be imputed, except for CCI, in which case last observation carried forward (LOCF) will be utilized.

Efficacy and safety analyses will be based on nominal visits as recorded on the CRFs. The only exception will be the early termination (ET) visit if a subject terminates before completion of Week 15. If the subject terminates before Week 15, the data collected at the early termination visit will be assigned to the closest planned visit (target day) for that efficacy or safety assessment. If the early termination visit is equidistant to 2 visits, it will be assigned to the later visit. If the early termination visit is associated with a visit that already exists, the non ET visit will be the representative visit. However, for purposes of LOCF, if more than one value is in a visit window the latter value will be used to carry forward. For all safety categorical determinations, early termination and unplanned visits are considered even if they are not assigned to a visit.

If a subject is missing Baseline (eg, Day 0), the last measurement, taken prior to first exposure to the investigational product, will be used.

Concentrations below the limit of quantification

In all data presentations (except listings), concentrations below the limit of quantification (BLQ) will be set to zero. (In listings BLQ values will be reported as “<LLQ”, where LLQ will be replaced with the value for the lower limit of quantification).

Deviations, missing concentrations and anomalous values

In summary tables and plots of median profiles, statistics will be calculated having set concentrations to missing if 1 of the following cases is true:

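### The planned PWC-20 summaries separate withdrawal symptoms poorly from on-drug or disease symptoms and can exclude withdrawal only weakly; a paired Day 105 to Day 119 summary would help (minor)

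*SAP*

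**What the plan says.** SAP 6.6.9 plans two summaries. The first is symptom incidence: "Summaries of the count and percentage of patients experiencing each symptom and severity listed in the PWC-20 will be provided by treatment group", in the adverse-event reporting format. The second is the total score: "The Total PWC-20 score will be presented by treatment group using continuous summary statistics for the raw data". Neither names a visit, a reference reading or a change score. The section just before it (SAP 6.6.8, QUIP-RS) does ask for baseline, absolute and change values at each time point.

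On timing, SAP 3.5.9 says "The PWC-20 is collected after the completion of study treatment and also at the first visit of follow-up". The protocol performs the checklist at the Day 105 visit (6.2.12), at the Day 119 follow-up visit (6.3) and at early termination (6.6). No pre-treatment reading is planned.

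Three other provisions bear on those readings:

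- The heading of Protocol 6.2.2 is "Dosing: Day 1 through Day 105", and a Schedule of Activities footnote says "Subjects take their morning dose at home".
- For early terminators, SAP 5.3 says "the data collected at the early termination visit will be assigned to the closest planned visit (target day) for that efficacy or safety assessment".
- On who attends Day 119, Protocol 3.1.4 says "Subjects not directly entering study B7601017 at Week 15 must complete the Week 17 and Week 19 Follow-up visits". Direct entrants leave this study at Week 15 and continue treatment.

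Protocol 7.2.8 gives the interpretive standard: "a combination of symptoms and time course, not type of symptoms alone, best differentiate between discontinuation symptoms of rebound/withdrawal and return of anxiety".

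**The concern.** The protocol says withdrawal is recognised by symptoms together with their time course. The planned summaries keep the symptoms and largely drop the time course. Taken at face value, the SAP 3.5.9 description invites on-drug symptoms at Day 105 to be read as discontinuation symptoms. Early terminators, some of whom are assessed after stopping, are averaged into that same on-drug column. The Day 119 column then describes a different and self-selected group.

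The PWC-20 is a named secondary safety endpoint (Protocol 2.4.2.1). At stake is whether its tables can support a statement about discontinuation effects in either direction.

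**Working it through.** **1. Denominators.** The documents give no figure for the PWC-20, so I start from the planned arm sizes. Protocol 9.1: 32 / 0.9 = 35.6, rounded up to 36 per arm, as stated. Using the Cohort 1 and Cohort 2 ratios:

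- 15 mg: 54 × 2/3 + 144 × 1/8 = 36 + 18 = 54
- Placebo: 54 × 1/3 + 144 × 1/8 = 18 + 18 = 36
- 1, 3 and 7 mg: 144 × 2/8 = 36 each
- Total: 54 + 4 × 36 = 198, as stated

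**2. Is Day 105 on drug?** Protocol 1.4.3 gives a half-life of 21.0 to 22.4 h after single doses. The fraction remaining is 0.5^(t / half-life).

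- 4 h after a dose: 0.876 to 0.884
- 24 h after a dose: 0.453 to 0.476

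Even if the last dose had been the previous morning, 45% to 48% would remain. The single-dose half-life implies steady-state accumulation of 1/(1 − 0.453) = 1.83 to 1/(1 − 0.476) = 1.91. That agrees with the roughly 2-fold accumulation reported in the same section, so using it at steady state is reasonable. Day 105 is an on-drug reading.

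**3. Where do early-termination scores go?** The planned PWC-20 days are 105 and 119, with midpoint 112. Every termination day from 1 to 104 is nearer to 105, so 104 of 104 map to Day 105 and none to Day 119. Protocol 6.6 also lists, among the termination assessments, a review of the diary for the time since dosing stopped. Some of these readings are therefore off drug.

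**4. Change in case mix between visits.** Let r be the fraction of completers who roll over, a their mean score, and b the mean of the rest. With no withdrawal effect and no change within any subject:

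- Day 105 mean = r·a + (1 − r)·b
- Day 119 mean = b
- Apparent shift = r·(b − a), while the paired change is 0

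Illustration with assumed values a = 6, b = 10, r = 0.6: Day 105 mean = 0.6 × 6 + 0.4 × 10 = 7.6, Day 119 mean = 10.0, shift +2.4. For r from 0.3 to 0.8 with the same 4-point gap, the shift is 0.3 × 4 = +1.2 to 0.8 × 4 = +3.2. None of these inputs is in the documents.

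This is a within-arm shift. The contrast with placebo is distorted by r·(b − a) on drug minus r·(b − a) on placebo, which is zero if rollover and gap are the same in both arms.

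**5. How late is Day 119?** Fourteen days is 336 h: 336 / 22.4 = 15.0 and 336 / 21.0 = 16.0 half-lives. With the ±3-day window and a last dose on Day 105, the range is 11 × 24 / 22.4 = 11.8 to 17 × 24 / 21.0 = 19.4. Five half-lives pass in 4.4 to 4.7 days. If the half-life were twice as long, 14 days would still be 7.5 to 8 half-lives. Day 119 is clearly off drug, but late for symptoms that Protocol 7.2.8 describes as early and short-lived.

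**6. What could zero cases at Day 119 exclude?** Assume 10% dropout, borrowed from Protocol 9.1, where it refers to non-evaluable subjects and dropouts before Week 5. The rollover rate is unknown, so it is varied. The one-sided 95% upper bound with zero events is 1 − 0.05^(1/n).

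| Rollover | n, 36-subject arm | Upper bound | n, 54-subject arm | Upper bound |
|---|---|---|---|---|
| 0% | 32 | 8.9% | 49 | 5.9% |
| 25% | 24 | 11.7% | 37 | 7.8% |
| 50% | 16 | 17.1% | 24 | 11.7% |
| 75% | 8 | 31.2% | 12 | 22.1% |
| 90% | 3 | 63.2% | 5 | 45.1% |

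**The case against.** The strongest reply is that the trial is randomized and the tables are by treatment group. Day 119 is a true off-drug reading with a concurrent placebo arm, so an excess on drug could be seen without any change score. SAP 6.6.9 plans symptom incidence and severity as well as totals, and SAP 5.2 says every visit will be represented in by-time-point statistics. Adverse events are collected at Days 119 and 133, and Protocol 8.3 counts signs of drug withdrawal among them. This stands, and it limits the point. It does not remove it. Showing both visits still gives two columns of different subjects, with early terminators inside the first. The SAP reports adverse events overall, for Period A and for Period B (3.5.1, 6.6), with no separate post-treatment summary.

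Second, the Day 105 label is partly a matter of words: the visit may follow the last morning dose, and the SAP never says its symptoms will be called withdrawal. That is fair, but the column still needs an accurate label.

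Third, subjects who continue treatment cannot show withdrawal, so their absence at Day 119 is inherent. A paired analysis uses the same selected subset and cannot recover symptoms that resolved before Day 119. Both statements are correct. Pairing removes the case-mix shift between visits and nothing more.

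Fourth, the effect of pooling early terminators cannot be sized. The documents give neither their number nor the time from last dose to the termination visit.

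**Conclusion.** The point holds as a minor one. As planned, the PWC-20 summaries poorly separate withdrawal symptoms from on-drug or disease symptoms. They can exclude withdrawal only weakly: in a 36-subject arm, zero cases at Day 119 would leave an upper bound between 8.9% (no rollover) and 63.2% (90% rollover), assuming 10% dropout.

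Two stronger readings are tempting and not supported:

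- A reader might infer that the checklist can neither show nor exclude withdrawal. The off-drug Day 119 reading with its placebo comparison, together with adverse-event collection, contradicts that.
- A reader might take the +1.2 to +3.2 shift as an expected bias. It rests on assumed rollover rates and an assumed score gap. It is a within-arm shift, and it reaches the comparison with placebo only if rollover or selection differs by arm, which the documents do not show.

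Severity is minor because the endpoint is descriptive and plays no part in the decision criteria of SAP 5.1.2.

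**What to change.** Amend SAP 3.5.9 and 6.6.9, with a matching exception in SAP 5.3, before unblinding:

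- Label Day 105 as the end-of-treatment, on-drug reference, and present Day 105 and Day 119 separately.
- Add, by arm and against placebo, the within-subject change from Day 105 to Day 119 in total score, and the count of subjects with new or worsened items. Restrict this to subjects who stopped drug and have both readings. Both measures are needed because fading side effects can offset new symptoms in a total.
- Exempt the PWC-20 from the early-termination mapping and tabulate those scores separately by days since last dose.
- Report Day 119 denominators by extension entry in each arm.
- State that Day 119, about two weeks after the last dose in a self-selected subset, cannot rule out early, short-lived symptoms.

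The cost is SAP wording and one extra table, with no new data. The paired summary will have fewer subjects than the Day 105 table. The late timing and the selection of subjects who do not roll over can be stated but not cured by this change.
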